4.0 Study Design

4.1 Describe and explain the study design (e.g. case-control, cross-sectional, ethnographic, experimental, interventional, longitudinal, observational).

Response: This investigation will be a prospective, randomized, double blind, placebo controlled parallel design study conducted in patients with type 1 diabetes. The study will be conducted at Diabetes-Endocrinology Center of WNY, affiliated to the State University of New York at Buffalo.

84 overweight or obese patients with type 1 diabetes on treatment with either continuous subcutaneous insulin infusion (CSII; also known as insulin pump) or multiple (four or more) injections of insulin per day will be included in the study. They will be randomized into 2 groups of 42 patients each. The patients will be randomized to daily subcutaneous injections of placebo or liraglutide. In view of the possibility of hypoglycemia and the side effect of nausea all patients will be started on 0.6 mg of liraglutide per day. The dose will then be titrated up to 1.8 mg.

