6.0 Inclusion and Exclusion Criteria

6.1 Describe the criteria that define who will be **included** in your final study sample.

NOTE: This may be done in bullet point fashion.

Response:

- 1) Type 1 Diabetes on continuous subcutaneous insulin infusion (CSII; also known as insulin pump) or multiple (four or more) injections of insulin per day.
- 2) Using a continuous glucose monitoring device (CGM) or regularly measuring their blood sugars four times daily.
- 3) HbA1c of less than 10.0%.
- 4) Well versed with carbohydrate counting.
- 5) Age 18-80 years
- 6) $BMI \geq 25 \text{ kg/m}^2$
- 7) Age at diagnosis of type 1 diabetes should be <30 years.
- 8) Evidence of auto-immunity to beta cells (GAD-65 and islet cell antibody screen)

6.2 Describe the criteria that define who will be **excluded** from your final study sample.

NOTE: This may be done in bullet point fashion.

Response: 1) Type 1 diabetes for less than 6 months;
2) Coronary event or procedure (myocardial infarction, unstable angina, coronary artery bypass, surgery or coronary angioplasty) in the previous four weeks;
3) Hepatic disease (transaminase > 3 times normal) or cirrhosis;
4) Renal impairment (serum eGFR $<30 \text{ ml/min/1.73m}^2$);
5) HIV or Hepatitis B or C positive status;
6) Participation in any other concurrent clinical trial;
7) Any other life-threatening, non-cardiac disease;
8) Use of an investigational agent or therapeutic regimen within 30 days of study.
9) history of pancreatitis
10) pregnancy
11) inability to give informed consent
12) history of gastroparesis

- 13) history of medullary thyroid carcinoma or MEN 2 syndrome.
- 15) Use of any agent other than insulin for treatment of diabetes (metformin, pramlintide or thiazolidinediones;
- 16) painful gallstones;
- 17) alcoholism;
- 18) hypertriglyceridemia (>500 mg/dl)
- 19) History of pancreatitis

6.3 Indicate specifically whether you will include any of the following special populations in your study using the checkboxes below.

NOTE: Members of special populations may not be targeted for enrollment in your study unless you indicate this in your inclusion criteria.

Response: None of the below populations will be enrolled

- Adults unable to consent
- Individuals who are not yet adults (infants, children, teenagers)
- Pregnant women
- Prisoners

6.4 Indicate whether you will include non-English speaking individuals in your study. **Provide justification if you will exclude non-English speaking individuals.**

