8.0 Eligibility Screening

8.1 Describe screening procedures for determining subjects' eligibility.

Screening refers to determining if prospective participants meet inclusion and exclusion criteria.

- Include all relevant screening documents with your submission (e.g. screening protocol, script, questionnaire).

Response: :

Prospective participants will be asked to read and understand the consent and any questions they may have regarding the protocol will be answered. If the subject wants to participate in the study, they will be asked to sign the informed consent form. The subject's medical history and current medications will be obtained as well as their blood pressure and vitals. A physical examination will also be done. Fasting labs before 10:00am include; CBC, CMP, HbA1c, lipid panel, C-peptide and GAD-6 and a urine pregnancy test. Blood samples of patients with negative GAD-65 antibodies will be screened for islet cell antibodies, if patient had evidence of auto- immunity to beta cells in the past, they will be retested during screening. Patients with no evidence of autoimmunity to beta cells will not be included in this trial. Patients meeting all the inclusion and exclusion criteria based on all screening tests will be enrolled in the study.

- N/A:** There is no screening as part of this protocol.

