20.0 Withdrawal of Subjects

N/A: This study is not enrolling subjects. This section does not apply.

20.1 Describe **anticipated** circumstances under which subjects may be withdrawn from the research without their consent.

Response: Pregnancy, DKA, severe and frequent hypoglycemia and drug intolerance (severe nausea and/or vomiting) developing any of the exclusionary condition listed in the inclusion and exclusion criteria.

The principal investigator of the study can remove a participant from the research study without their approval if for any reason he/she feels is appropriate, including: severe side effect, injury or medical condition which may place the patient at risk of further complications if patient continues to participate, failure to take the medication as instructed, failure to keep your scheduled appointments, cancellation of the study by the sponsor, or other administrative reasons.

Participation in this research study is voluntary. Subjects have the right to refuse to participate or to withdraw from participation at any time for any reason. Refusal to participate or withdrawal from the study will involve no penalty or loss of entitled benefits, nor affect the subjects ongoing medical care

20.2 Describe any procedures for orderly termination.

NOTE: Examples may include return of study drug, exit interview with clinician. Include whether additional follow up is recommended for safety reasons for physical or emotional health.

Response: If a subject withdraws from the research, the data collected to that point will be used toward the research finding. If applicable the subject will have to bring back any unused research drug and or device. If necessary, they will be asked to complete an end of study visit for their safety.

20.3 Describe procedures that will be followed when subjects withdraw from the research, including retention of already collected data, and partial withdrawal from procedures with continued data collection, as applicable.

Response: If a subject withdraws from the research, the data collected to that point will be used toward the research finding. Patients are allowed to withdraw from some procedures while continuing to participate in the study (take study medication). Efficacy and safety data will continue to be collected for the parts of study that patients agree to participate in.

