21.0 Risks to Subjects

21.1 List the reasonably foreseeable risks, discomforts, hazards, or inconveniences to the subjects related to their participation in the research. Consider physical, psychological, social, legal, and economic risks. Include a description of the probability, magnitude, duration, and reversibility of the risks.

NOTE: Breach of confidentiality is always a risk for identifiable subject data.

Response:

Subjects who experience severe nausea or vomiting after starting liraglutide will discontinue the study. Those with mild or moderate nausea will continue for at least one more week. If they continue to experience significant nausea (defined as interfering with normal activities), they will discontinue the study.

Subjects who develop pancreatitis will be withdrawn from the study.

Subjects who develop a new thyroid tumor during the study will be withdrawn. Patients will be informed that they should let study investigators know if they develop any swelling in the neck.

For the entire duration of the study, the patients will maintain a diary to record any hypoglycemia and other untoward side effects like nausea, changes in appetite and other experiences. Patients will be instructed to call the Diabetes Center to speak to a study investigator directly in case of any problem or untoward side effects. They will be specifically asked to call if they have hypoglycemia (blood sugar <70 mg/dl) or hyperglycemia (blood sugar >250 mg/dl) on more than one occasion. The target blood glucose during the study will be between 70-180mg/dl at all times, without increasing the incidence of blood glucose < 70 mg/dl.

The following Information from the boxed warning in the package insert regarding the risk of thyroid c-cell tumors will be discussed in details with all participating subjects:

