"Liraglutide causes dose-dependent and treatment-duration-dependent thyroid C-cell tumors at clinically relevant exposures in both genders of rats and mice. It is unknown whether Liraglutide causes thyroid C-cell tumors, including medullary thyroid carcinoma (MTC), in humans, as human relevance could not be ruled out by clinical or nonclinical studies. Liraglutide is contraindicated in patients with a personal or family history of MTC and in patients with Multiple Endocrine Neoplasia syndrome type 2 (MEN 2). Based on the findings in rodents, monitoring with serum calcitonin or thyroid ultrasound was performed during clinical trials, but this may have increased the number of unnecessary thyroid surgeries. It is unknown whether monitoring with serum calcitonin or thyroid ultrasound will mitigate human risk of thyroid C-cell tumors."

In addition, the following FDA text regarding the risk of developing fibrosarcomas will be discussed with all participating subjects

"In a 2-year repeat subcutaneous dose carcinogenicity study of liraglutide injected once a day in CD-1 mice, a treatment-related increase in fibrosarcomas was seen on the dorsal skin and subcutis, the body surface used for drug injection, in males in the 3 mg/kg/day group. These fibrosarcomas were attributed to the high local concentration of drug near the injection site. The liraglutide concentration in the clinical formulation (6 mg/mL) is 10 times higher than the concentration in the formulation used to administer 3 mg/kg/day liraglutide to mice in the carcinogenicity study (0.6 mg/mL)".

21.2 Describe procedures performed to lessen the probability or magnitude of risks, including procedures being performed to monitor subjects for safety.

Response: For the entire duration of the study, the patients will maintain a diary to record any hypoglycemia and other untoward side effects like nausea, changes in appetite and other experiences. Patients will be instructed to call the Diabetes Center to speak to a study investigator directly in case of any problem or untoward side effects. They will be specifically asked to call if they have hypoglycemia

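### Exclusion 13 does not cover a family history of medullary thyroid carcinoma, although the boxed warning quoted in section 21.1 contraindicates liraglutide for it

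*Combined protocol and SAP*

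**What the plan says.** Section 6.2, item 13, excludes a "history of medullary thyroid carcinoma or MEN 2 syndrome". It does not mention relatives, and neither does any other visible criterion in section 6.

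Section 21.1 reproduces the boxed warning from the package insert, which includes the statement "Liraglutide is contraindicated in patients with a personal or family history of MTC". The same sentence also contraindicates the drug in patients with MEN 2. The protocol's use of this warning is that the information "regarding the risk of thyroid c-cell tumors will be discussed in details with all participating subjects". Section 21.2 lists that discussion again among the measures to lessen risk.

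Section 8.1 describes screening as the subject's medical history, current medications, vital signs, physical examination and laboratory tests, and then gives the enrolment rule: "Patients meeting all the inclusion and exclusion criteria based on all screening tests will be enrolled in the study". Section 5.2 says that all qualified patients are randomised, up to 84. Section 20.1 allows withdrawal for "developing any of the exclusionary condition listed in the inclusion and exclusion criteria" and also gives the principal investigator a general discretion to remove a participant.

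**The concern.** The eligibility rule and the warning that the protocol itself quotes disagree on who may receive the drug. A patient who has neither MTC nor MEN 2, but whose relative had MTC, meets the written criteria. If allocated to liraglutide, that patient would take a drug that the quoted warning contraindicates for them.

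Entry is the place where this should be caught. The quoted warning says it is not known whether calcitonin or thyroid ultrasound monitoring reduces the risk in humans, and the protocol schedules neither. Protection during the study consists of patients reporting neck swelling and withdrawal after a new thyroid tumour (section 21.1). Section 22.1 expects no benefit to individual participants, so the protocol offers nothing to set against the exposure.

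**Working it through.** **Comparison of the texts.** The protocol gives no figure to reproduce on this point. The check sets the groups named in the warning against the exclusion list.

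| Group contraindicated in the warning quoted in 21.1 | Covered by a visible criterion in 6.2? |
|---|---|
| Personal history of MTC | Yes, item 13 |
| Family history of MTC | No |
| MEN 2 in the patient | Yes, item 13 |

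Item 13 does not contain the word personal, so its scope has to be read from context. It has the same form as "history of gastroparesis" and the pancreatitis items, which refer to the patient's own condition. The warning itself separates personal from family history. The personal reading is therefore the natural one.

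**Whether another step closes the gap.**

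- Screening (8.1 and the screening visit in 10.1): the subject's medical history is taken. Family history is not mentioned.
- Enrolment (5.2, 8.1): patients who meet the listed criteria are enrolled and randomised.
- Discussion of the warning (21.1, 21.2): it informs patients, but no rule turns the answer into an exclusion.
- Withdrawal (20.1): the list-based rule applies to a listed condition that develops on study. Family history of MTC is not listed and is not something that develops on study.

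What remains is physician judgement at screening and the investigator's general discretion.

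**Size.** Inputs: 84 patients, for whom section 4.1 says "They will be randomized into 2 groups of 42 patients each"; maximum dose 1.8 mg daily (10.1); 26 weeks of treatment (11.2). The proportion *q* with a family history of MTC is not in the documents. The range 0.1% to 1% is an assumption.

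Expected number enrolled = 84*q*. Expected number on liraglutide = 42*q*. Chance of at least one on liraglutide = 1 − (1 − *q*)^42.

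| *q* (assumed) | Expected enrolled | Expected on liraglutide | Chance of at least one on liraglutide |
|---|---|---|---|
| 0.1% | 0.08 | 0.04 | 1 − 0.999^42 = 4.1% |
| 0.5% | 0.42 | 0.21 | 1 − 0.995^42 = 19.0% |
| 1% | 0.84 | 0.42 | 1 − 0.99^42 = 34.4% |

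As a conditional illustration only: if *k* such patients were enrolled, the expected number on liraglutide is *k* × 42/84, and the chance that at least one receives it is 1 − C(84 − *k*, 42)/C(84, 42).

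- *k* = 1: 0.5 expected; 1 − 42/84 = 50%.
- *k* = 2: 1.0 expected; 1 − (42 × 41)/(84 × 83) = 75%.
- *k* = 3: 1.5 expected; 1 − (42 × 41 × 40)/(84 × 83 × 82) = 88%.

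Under the assumed range, two or more such enrolments have a probability of only about 0.3% to 21%, so the last two lines describe unlikely cases.

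**The case against.** The strongest case on the other side has four parts.

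- **Wording.** Item 13 does not say that only the patient's own history counts, so a screener could read it more broadly. That is true, but an exclusion for a contraindication should not depend on how the screener reads it.
- **Unseen material.** The numbering jumps from 13 to 15, directly after the MTC item, so an item 14 may have been lost when the text was extracted. The consent pages were removed from the public copy, and the telephone screening form named in 16.1 is not included. Any of these could deal with family history. This has to be disclosed and limits certainty. However, nothing in the visible text suggests that it is so, and pancreatitis appears twice in the list, which makes an editing slip an equally possible reason for the jump.
- **Mitigation.** The warning is to be discussed in detail, and the protocol counts this as a risk-reducing measure. If it takes place at consent, before the medical history is taken, a patient might mention an affected relative in time. The investigator could then act. This lowers the practical risk but does not supply a rule.
- **Small effect.** The expected number exposed is below one across the assumed range, and the warning says it is unknown whether the drug causes these tumours in humans. Both points stand. They bear on the expected harm and do not remove the contraindication.

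**Conclusion.** The concern holds. As written, the criteria admit a patient whom the protocol's own quoted warning says should not receive liraglutide, and no visible step prevents it. The conclusion rests on reading item 13 as personal history and on no missing item 14 covering relatives.

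The number of patients at issue is small: an expected 0.04 to 0.42 on liraglutide if 0.1% to 1% have such a family history, a range that the documents neither support nor contradict. Each such patient enrolled would have a 1 in 2 chance of receiving the drug, for up to 26 weeks at up to 1.8 mg daily. The point should be fixed for patient safety. It has no bearing on the primary analysis, the sample size or the trial's conclusions.

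**What to change.** Reword exclusion 13 so that it covers MTC in the patient or in a family member, and MEN 2 in the patient. Add a question on family history of MTC to the medical history at the screening visit (8.1 and 10.1), and confirm that the telephone screening form asks it too. State whether an item 14 exists and what it says. If patients are already enrolled, ask them the same question.

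The cost is one line in section 6.2 and one question at screening. Design, sample size and analysis stay as they are.

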7.0 Vulnerable Populations

If the research involves special populations that are considered vulnerable, **describe the safeguards included to protect their rights and welfare.**

NOTE: You should refer to the appropriate checklists, referenced below, to ensure you have provided adequate detail regarding safeguards and protections. You do not, however, need to provide these checklists to the IRB.

7.1 For research that involves **pregnant women**, safeguards include:

NOTE CHECKLIST: Pregnant Women (HRP-412)

Response: We will not be using subjects from vulnerable populations

N/A: This research does not involve pregnant women.

7.2 For research that involves **neonates of uncertain viability or non-viable neonates**, safeguards include:

NOTE CHECKLISTS: Non-Viable Neonates (HRP-413), or Neonates of Uncertain Viability (HRP-414)

Response:

N/A: This research does not involve non-viable neonates or neonates of uncertain viability.

7.3 For research that involves **prisoners**, safeguards include:

NOTE CHECKLIST: Prisoners (HRP-415)

Response:

N/A: This research does not involve prisoners.

7.4 For research that involves **persons who have not attained the legal age for consent to treatments or procedures involved in the research (“children”)**, safeguards include:

NOTE CHECKLIST: Children (HRP-416)

Response:

N/A: This research does not involve persons who have not attained the legal age for consent to treatments or procedures (“children”).

7.5 For research that involves **cognitively impaired adults**, safeguards include:

NOTE CHECKLIST: Cognitively Impaired Adults (HRP-417)

Response:

N/A: This research does not involve cognitively impaired adults.

7.6 Consider if other specifically targeted populations such as students, employees of a specific firm, or educationally or economically disadvantaged persons are vulnerable. **Provide information regarding their safeguards and protections, including safeguards to eliminate coercion or undue influence.**

Response: No specific populations or vulnerable groups will be targeted. All subjects enrolled in this study will be of legal adult consenting age with the ability to speak, read and interrupt the English language. Patients will have the ability to speak with the research team regarding any questions or concern they have before signing the consent. Patients are made aware that this study is voluntary and they are able to stop participating at any time they feel uncomfortable. Patients are not

be pressured into participating and their clinic standard of care will remain the same if they participate or choose not to participate.

8.0 Eligibility Screening

8.1 Describe screening procedures for determining subjects' eligibility.

Screening refers to determining if prospective participants meet inclusion and exclusion criteria.

- Include all relevant screening documents with your submission (e.g. screening protocol, script, questionnaire).

Response: :

Prospective participants will be asked to read and understand the consent and any questions they may have regarding the protocol will be answered. If the subject wants to participate in the study, they will be asked to sign the informed consent form. The subject's medical history and current medications will be obtained as well as their blood pressure and vitals. A physical examination will also be done. Fasting labs before 10:00am include; CBC, CMP, HbA1c, lipid panel, C-peptide and GAD-6 and a urine pregnancy test. Blood samples of patients with negative GAD-65 antibodies will be screened for islet cell antibodies, if patient had evidence of auto- immunity to beta cells in the past, they will be retested during screening. Patients with no evidence of autoimmunity to beta cells will not be included in this trial. Patients meeting all the inclusion and exclusion criteria based on all screening tests will be enrolled in the study.

- N/A:** There is no screening as part of this protocol.

9.0 Recruitment Methods

- N/A:** This is a records review only, and subjects will not be recruited. NOTE: If you select this option, please make sure that all records review procedures and inclusion/exclusion screening are adequately described in other sections.

9.1 Describe when, where, and how potential subjects will be recruited.

NOTE: Recruitment refers to how you are identifying potential participants and introducing them to the study. Include specific methods you will use (e.g. searching charts for specific ICD code numbers, Research Participant Groups, posted advertisements, etc.).

Response: Participants will be identified by prescreening clinical charts, patient doctor interaction at the time of their visits, flyers advertisements and researchmatch.org. Diabetes Endocrinology Center of WNY Locations include:

1. [name]
2. [name]
3. [name]

The study clinical team will evaluate their clinic patients for possible participation in this study according to the inclusion and exclusion criteria at the Diabetes and

Endocrinology Center of WNY. Patients that may qualify for the study are referred to the research team for further eligibility evaluation. Patients meeting the inclusion and exclusion criteria based on preliminary phone evaluation will be invited to participate in the study.

9.2 Describe how you will protect the privacy interests of prospective subjects during the recruitment process.

NOTE: Privacy refers to an individual's right to control access to him or herself.

Response: Patient charts will be screened according to the study inclusion and exclusion criteria by our trained clinical staff and physicians. If the patient qualifies and is of consenting age, the physicians will speak to them about their interests in participating in research. If the patient agrees, their information will be given to the research coordinator to be contacted for further evaluation. All personal information will be kept confidential and locked in the coordinator office.

9.3 Identify any materials that will be used to recruit subjects.

NOTE: Examples include scripts for telephone calls, in person announcements / presentations, email invitations.

 For advertisements, include the final copy of printed advertisements with your submission. When advertisements are taped for broadcast, attach the final audio/video tape. NOTE: You may submit the wording of the advertisement prior to taping to ensure there will be no IRB-required revisions, provided the IRB also reviews and approves the final version.

Response: In addition to screening clinical charts, participations will be identified through; flyer advertisement and researchmatch.org

